8.4.2 Procedures for Recording and Reporting Adverse Events

The Medicines for Human Use (Clinical Trials) Regulations 2004 and Amended Regulations 2006 gives the following definitions:

Adverse Event (AE): Any untoward medical occurrence in a subject to whom a medicinal product has been administered including occurrences which are not necessarily caused by or related to that product.

Adverse Reaction (AR): Any untoward and unintended response in a subject to an investigational medicinal product which is related to any dose administered to that subject.

Unexpected Adverse Reaction (UAR): An adverse reaction the nature and severity of which is not consistent with the information about the medicinal product in question set out in:

The Investigator's Brochure (IB) relating to the study.

Serious adverse Event (SAE), Serious Adverse Reaction (SAR) or Suspected Unexpected Serious Adverse Reaction (SUSAR): Any adverse event, adverse reaction or unexpected adverse reaction, respectively, that

> Results in death; Is life-threatening; Required hospitalisation or prolongation of existing hospitalisation; Results in persistent or significant disability or incapacity; Consists of a congenital anomaly or birth defect.

Important Medical Events (IME) & Pregnancy

Events that may not be immediately life-threatening or result in death or hospitalisation but may jeopardise the patient or may require intervention to prevent one of the other outcomes listed in the definition above should also be considered serious.

Although not a serious adverse event, any unplanned pregnancy will also be reported via the SAE reporting system. Women who become pregnant within the study will be followed up with evaluation of the pregnancy, foetus and child.

Time period for collection of adverse events

AEs will be recorded from the randomisation visit to the final safety visit (day 212). Any AEs that are unresolved at the follow-up visit in the study will be followed up by the

investigator for as long as medically indicated, but without further recording in the SDW. The following information will be collected for each AE: 1) AE (verbatim); 2) the date and time when the AE started and stopped; 3) maximum intensity (see definitions of intensity below); 4) whether the AE is serious or not; 5) investigator causality rating against the Investigational Product (yes or no); 6) action taken with regard to Study intervention (IMP/Placebo); 7) AE caused patient's withdrawal from study (yes or no); 8) outcome.

In addition, the following variables will be collected for SAEs: 1) date AE met criteria for serious AE; 2) date Investigator became aware of serious AE; 3) Reason why AE is deemed serious; 4) date of hospitalisation; 5) date of discharge; 6) probable cause of death; 7) date of death; 8) autopsy performed; 9) causality assessment in relation to CBD; 10) causality in relation to any other medication if relevant; 11) description of AE.

Intensities will be reported for each AE under the following categories:

- mild (awareness of sign or symptom, but easily tolerated)
- moderate (discomfort sufficient to cause interference with normal activities)
- severe (incapacitating, with inability to perform normal activities)

Causality

The Investigator will assess causal relationship between Cannabidiol and each AE, and answer "yes" or "no" to the question "Do you consider that there is a reasonable possibility that the event may have been caused by the investigational product?" For SAEs, if felt necessary by the treating team, the patient's allocation to Cannabidiol or placebo will be decoded by contacting the 24 hours emergency unblinding service and the causal relationship will also be assessed for any other medications if relevant.

Detecting adverse events

Participants will be asked the open question "Have you had any health problems since you were last asked?" to evoke spontaneous reports of side-effects. Spontaneous and self-rated side-effects will be evaluated for intensity and seriousness. Deterioration in lab or examination safety measures will be recorded as AE if they are associated with symptoms or signs or if they are sufficiently marked to be clinically significant. Suicidal thoughts, acts or events are AEs that will be rated and recorded. All such events will be notified to the clinical team and carefully monitored by them. Worsening symptoms of the primary study condition will not be recorded as an AE. However, if hospitalization results from worsening of the primary study condition, the hospitalization will be reported as an SAE. Diagnoses will be recorded rather than symptoms, signs or lab parameters.

Reporting and follow-up of adverse events

All SAEs have to be reported, whether or not considered causally related to the trial medication. All SAEs will be recorded in the source data worksheet (SDW). If any SAE occurs in the course of the study, then investigators or other site personnel will inform the local Principal Investigator and clinician for that patient immediately; i.e. within one business day... All completed SAE forms will be filed appropriately in the Investigator Site File (ISF) and as required within the SDW Study Folder. The participant will be followed up by the medic until the event or reaction has reached an outcome. The participant's GP will be contacted by the PI or delegate, if it is medically indicated to do

SO.

Reporting Responsibilities

King's College London and the South London & Maudsley NHS Foundation trust have delegated the delivery of the Sponsor's responsibility for Pharmacovigilance (as defined in Regulation 5 of the Medicines for Human Use (Clinical Trials) Regulations 2004 to the King's Health Partners Clinical Trials Office (KHP-CTO).

All SAEs, SARs and SUSARs (excepting those specified in this protocol as not requiring reporting) will be reported immediately (and certainly no later than 24hrs) by the Investigator to the KHP-CTO and CI for review in accordance with the current Pharmacovigilance Policy.

The KHP-CTO will report SUSARs to the regulatory authorities (MHRA, competent authorities of other EEA (European Economic Area) states in which the trial is taking place.

The Chief Investigator will report to the relevant ethics committee. Reporting timelines are as follows:

- SUSARs which are fatal or life-threatening must be reported no later than 7 days after the sponsor is first aware of the reaction. Any additional relevant information must be reported within a further 8 days.
- SUSARs that are not fatal or life-threatening must be reported within 15 days of the sponsor first becoming aware of the reaction.
- The Chief Investigator and KHP-CTO (on behalf of the co-sponsors), will submit a Development Safety Update Report (DSUR) relating to this trial IMP, to the MHRA and REC annually.

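### Section 8.4.2 takes worsening of the study condition out of adverse event recording and restores only hospitalised cases, which fits neither its own seriousness criteria nor the list in 8.4.2.2

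*Protocol*

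**What the plan says.** Section 8.4.2 of the protocol defines an AE broadly: "Any untoward medical occurrence in a subject to whom a medicinal product has been administered", related to the product or not. The SAE definition builds on it. It opens "Any adverse event, adverse reaction or unexpected adverse reaction, respectively, that" and lists "Results in death; Is life-threatening; Required hospitalisation or prolongation of existing hospitalisation; Results in persistent or significant disability or incapacity", followed by congenital anomaly. Under the subheading on important medical events, it adds that events without admission that "may jeopardise the patient or may require intervention to prevent one of the other outcomes listed in the definition above should also be considered serious".

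Under the subheading on detecting adverse events, the section then says "Worsening symptoms of the primary study condition will not be recorded as an AE". One exception follows: "However, if hospitalization results from worsening of the primary study condition, the hospitalization will be reported as an SAE". The sentences just before these keep suicidal ideation, acts and events inside AE recording.

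On reporting, 8.4.2 says "All SAEs have to be reported, whether or not considered causally related to the trial medication". Its paragraph on reporting responsibilities sets a 24-hour limit but excepts events that the protocol elsewhere names as exempt.

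Section 8.4.2.1 has every AE recorded on the source data worksheet (SDW). Section 8.4.2.2 lists anticipated AEs. Its first group, labelled as unrelated to the intervention and exempt from reporting, includes worsening psychotic symptoms, suicidal ideation and transition to a first episode of psychosis.

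**The concern.** The exclusion and the seriousness criteria do not cover the same ground. Admission is one of several outcomes that make an event serious, yet it is the only one that brings worsening of the study condition back into the safety data. Entry into the SAE record then depends on where the participant was cared for, not on how serious the episode was.

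Psychotic deterioration is the harm opposite in direction to the benefit the trial hopes to show, and safety and tolerability over six months is a stated objective. Section 12.9.4 gives the Data Monitoring Committee ongoing access to unblinded safety data. If serious worsening without admission is missing from the SAE data, the comparison of SAEs by arm is incomplete for the event type that matters most in this population.

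The document also gives two answers to a basic question: is worsening of psychosis an AE or not? Sites cannot follow both.

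**Working it through.** No arithmetic applies, and the protocol states no figure to reproduce. The check sets the passages against each other.

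**Step 1: an SAE must first be an AE.** The SAE definition begins from an adverse event or reaction ("Any adverse event, adverse reaction or unexpected adverse reaction, respectively, that"). Section 8.4.2 collects seriousness and investigator causality as items on the AE record. An occurrence that is not an AE is rated for neither. It cannot become a serious adverse reaction or a SUSAR, and it starts neither the 24-hour limit nor the 7-day and 15-day limits.

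**Step 2: go through the criteria for worsening without admission**, taking the exclusion in 8.4.2 as written.

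| Seriousness criterion in 8.4.2 | Route into SAE data without admission |
|---|---|
| Disability or incapacity | None stated |
| Important medical event (for example, intervention that averts admission) | None stated |
| Life-threatening, suicidal act | Covered: suicidal acts remain AEs |
| Life-threatening, other route | None stated |
| Death by suicide | Covered, as above |
| Death by another route | Gap only on a literal reading: the exclusion names symptoms, not deaths |

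The firm gaps are incapacity, important medical events, and life-threatening worsening that is not suicidal.

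**Step 3: compare with 8.4.2.1 and 8.4.2.2.** There are two readings.

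- *The exclusion in 8.4.2 governs.* Worsening is not an AE. Cases without admission are neither rated for seriousness nor reported.
- *Sections 8.4.2.1 and 8.4.2.2 govern.* Worsening and transition are AEs and go on the worksheet with a seriousness rating. They are also labelled unrelated in advance and exempt from reporting. The exception in the reporting-responsibilities paragraph refers to events the protocol names as exempt, so it can be read to release even serious worsening from the 24-hour limit.

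The second reading repairs recording but not reporting. On neither reading is serious worsening without admission certain to be reported, although the section says "All SAEs have to be reported, whether or not considered causally related to the trial medication".

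**Step 4: can the efficacy assessments stand in?** After baseline, the CAARMS is scheduled at about days 28, 91 and 182, so the later gaps are 91 − 28 = 63 days and 182 − 91 = 91 days. As described in section 8.2.1, its items rate severity, frequency, pattern and distress. It measures worsening by arm but does not classify an event as serious, does not ask about drug causality and starts no reporting limit.

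**The case against.** Keeping the efficacy endpoint out of AE recording is a deliberate choice. Worsening is measured by CAARMS in both arms at each visit through day 182. Section 6.7.2 makes transition a defined exit category, with safety outcomes still assessed. The committee sees unblinded safety data throughout. This argument stands for non-serious worsening, which need not be an AE. It does not reach serious worsening, for the reason in the last step of the check.

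Three stronger readings are tempting, and the document does not support them.

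- A reader might infer that all fatal and life-threatening worsening escapes. It does not: suicidal acts remain AEs and can be SAEs whether or not the participant is admitted. A death is in any case an untoward occurrence under the AE definition, and 8.4.2 collects date and probable cause of death for SAEs.
- A reader might infer that worsening is never recorded. That is one side of a contradiction: 8.4.2.1 and 8.4.2.2, taken together, have it recorded.
- A reader might size the gap from the background figure of about one-third developing psychosis within 3 years. That figure counts transitions. The gap concerns serious worsening without admission, which is a different set of events. Many transitions would not meet a seriousness criterion or would be admitted, and transitions are identified and followed in any case.

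It is also conjecture that the loss would differ between sites. The protocol describes no difference in admission practice.

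**Conclusion.** The concern holds in limited form. The hospitalisation-only exception in 8.4.2 does not match that section's own seriousness criteria for non-suicidal worsening managed outside hospital. The exclusion also contradicts 8.4.2.1 and 8.4.2.2 on whether worsening is an AE, and the exception to the 24-hour rule could release serious cases from reporting. The passages must be reconciled.

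The size cannot be computed: the protocol gives no rate of serious worsening and no share managed without admission. The number may be small. The point rests on the wording as it stands and assumes that sites follow it literally; an investigator might report such a case anyway. The Data Monitoring Committee charter and the pharmacovigilance policy that the protocol refers to were not available and might narrow the gap in practice, but they would not remove the contradiction in the protocol. This should be corrected because the safety comparison relies on it and the correction is cheap. It does not undermine the primary efficacy analysis.

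**What to change.** Amend 8.4.2, 8.4.2.1 and 8.4.2.2 together. Changing only the hospitalisation sentence would leave the exemption in 8.4.2.2, and the clause that refers to it, in force.

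1. In 8.4.2, replace the hospitalisation-only exception with a rule that worsening of the study condition, including transition to psychosis, that meets any seriousness criterion of that section (important medical events included) is recorded, assessed for causality and reported as an SAE.
2. In 8.4.2.2, state that the group exempt from reporting covers non-serious events only, so that the exception to the 24-hour rule cannot reach a serious event.
3. State once, and apply in all three sections, whether non-serious worsening is recorded as an AE or captured by CAARMS alone. Either is workable.

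The cost is a short protocol amendment, a note to sites and a few more SAE forms. No visit, assessment or treatment rule changes.

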8.4.2.1 Adverse events

AEs will not be reported unless there is a reasonable suspicion of effect from the medical treatment. All AEs will be recorded on the SDW.

8.4.2.2 Anticipated Adverse events

In this population of CHR-APS, we anticipate:

1. AEs not related to the study intervention, not needing reporting:

- Worsening of psychotic symptoms, sleep disturbances, appetite disturbances, anxiety symptoms, mood symptoms, and suicidal ideation

- Transition to FEP

2. AEs potentially related to the study intervention, needing reporting:

- Hepatic Disorders (elevations of liver transaminases)

- Gastrointestinal Disorders (diarrhoea, gastroenteritis, abdominal pain, discomfort, weight decreased)

- Nervous System Disorders (somnolence, sedation, lethargy, fatigue, malaise, asthenia, drooling, salivary hypersecretion, gait disturbance)

- Infections (viral infections, pneumonia, fungal infections)

- Hypersensitivity Reactions (pruritus, erythema, rash, angioedema, hypoxia, respiratory failure)

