8.4.3 Treatment Stopping Rules

The trial may be prematurely discontinued by the Sponsor, Chief Investigator or Regulatory Authority on the basis of new safety information or for other reasons given by the Data Monitoring & Ethics Committee / Trial Steering Committee, regulatory authority or ethics committee concerned.

If the trial is prematurely discontinued, active participants will be informed and no further participant data will be collected. The Competent Authority and Research Ethics Committee will be informed within 15 days of the early termination of the trial.

9 Participant timeline

With reference to the internal pilot as well as the RCT, the end of the trial will be defined as last patient last visit. Each individual subject will remain in the trial until the final visit, at month 7. This date will be 30 days after the study end-point (day 182). The total duration from first patient first visit to last patient last visit is anticipated to be 42 months.
10 Sample size

10.1. Proposed sample size:

1) Pilot study: 60 randomised within 12 months of the start of patient recruitment;

2) RCT: 300 hundred CHR-APS patients; n=150 per treatment arm

10.2. Sample size justification:

1) **Internal Pilot:** There was no powered sample size calculation for the internal pilot, the number is instead in line with suggested sample sizes for pilot and feasibility studies and is sufficient to estimate feasibility outcomes.

2) Phase IIB RCT

Justification of Effect Size (ES=0.4)

In our proof-of-concept studies, in which the effect size for 3 weeks of treatment with CBD (Mean change \pm SD: 12.87 \pm 12.8) compared to placebo (Mean change \pm SD: 7.64 \pm 12.6) on psychotic symptom severity was found with a standardised mean difference of 0.41.

The RCT has been powered for the primary outcome. For a novel intervention for CHR patients to be clinically meaningful, we have assumed that its effect-size should be comparable to, or greater than that of CBT, the treatment currently recommended for this group in the NICE guidelines ¹³. The effect size for the change in the severity of psychotic symptoms after 12 months of CBT in the trial by Morrison et al ¹² was 0.39 (estimated as standardized mean difference).

Sample Size Calculation

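### Section 8.4.2.2 settles causality in advance for seven anticipated event types, and the SAE exception in 8.4.2 can be read to exempt serious ones from immediate reporting

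*Protocol*

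**What the plan says.** Protocol 8.4.2.2 divides anticipated events into two lists. The first is headed "AEs not related to the study intervention, not needing reporting" and contains "Worsening of psychotic symptoms, sleep disturbances, appetite disturbances, anxiety symptoms, mood symptoms, and suicidal ideation" and, as a separate entry, "Transition to FEP". Nothing in the heading or the entries limits the list to non-serious events.

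Section 8.4.2 sets the general rules:

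- Causality: "The Investigator will assess causal relationship between Cannabidiol and each AE", as a yes/no answer.
- Suicidality: "Suicidal thoughts, acts or events are AEs that will be rated and recorded".
- Primary condition: worsening symptoms are not recorded as an AE, but a resulting hospitalisation is reported as an SAE.
- SAEs, under reporting and follow-up: "All SAEs have to be reported, whether or not considered causally related to the trial medication".
- SAEs, under reporting responsibilities: immediate reporting to the trials office (KHP-CTO) and the chief investigator covers "All SAEs, SARs and SUSARs (excepting those specified in this protocol as not requiring reporting").

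Section 8.4.2.1 makes onward reporting of an AE depend on a reasonable suspicion of a treatment effect, but has every AE recorded on the source data worksheet.

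Section 8.4.3 says that if the trial is discontinued early, "active participants will be informed and no further participant data will be collected". Section 8.4.2 has AEs recorded from randomisation to the final safety visit at day 212, and SAEs followed until they reach an outcome.

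**The concern.** Whether a listed event was caused by the study drug is a question about the individual case. In aggregate it is a question about the difference between arms. Section 8.4.2.2 answers it for a whole class of psychiatric events before any has occurred. Section 6.7.2 points the other way: it names emerging or worsening depression, suicidal thoughts and unusual mood or behaviour change as reasons for which an investigator may withdraw a participant.

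The greater risk lies in the SAE exception. The 7-day and 15-day SUSAR timelines in 8.4.2 start when the sponsor becomes aware, and awareness depends on the investigator's report. A site that reads the exception together with the list could treat a serious listed event as outside the immediate-reporting duty, and the clock would not start. For a drug given for up to 182 days to young people, many of whom will never develop a psychotic disorder, the text should leave no room for that reading.

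**Working it through.** No figure in the plan is at issue, so the check sets the sections side by side.

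**1. Scope of the list.** The first entry names six event types: worsening psychotic symptoms, sleep, appetite, anxiety and mood symptoms, and suicidal ideation. Transition is the seventh (6 + 1 = 7). All seven share the same advance classification.

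**2. Causality.** Section 8.4.2 asks for a judgement on each AE. Section 8.4.2.2 calls seven types of AE unrelated. Section 8.4.2.1 makes reporting turn on suspicion, and the list settles suspicion beforehand. An investigator who suspects the drug in a case of new suicidal ideation must report it under 8.4.2.1, yet 8.4.2.2 says it needs no reporting. This is a contradiction.

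**3. Serious events.** Three texts bear on a serious listed event, for example an admission after transition:

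- the general SAE rule in 8.4.2: report, whatever the causality;
- the hospitalisation sentence in 8.4.2: report as an SAE if it results from worsening of the primary condition;
- the exception in 8.4.2, read with 8.4.2.2: exempt, because the only named list of non-reportable events includes both worsening and transition and sets no limit on seriousness.

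The first two require a report and the third can be read to waive it. The exception also names SUSARs. By definition these are suspected reactions, so a list of events presumed unrelated cannot sensibly exempt them.

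**4. Recording of worsening.** Section 8.4.2 says worsening symptoms of the primary condition are not recorded as an AE. Section 8.4.2.2 calls worsening psychotic symptoms an AE, and 8.4.2.1 has every AE recorded. All three cannot hold.

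**5. Suicidal ideation.** Section 8.4.2 has it rated and recorded; 8.4.2.2 says it needs no reporting. Recording and onward reporting are different acts, so this is a tension and not a direct contradiction.

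**6. Early termination.** Section 8.4.2 records AEs to day 212, which is 212 − 182 = 30 days after the study end-point, and follows SAEs to outcome. Section 8.4.3 ends all participant data collection at discontinuation, including a stop made on new safety information. Section 3.2.2 gives an elimination half-life of 2 to 5 days, so exposure outlasts the last dose. The final safety visit is only a review of medical records (section 7.5).

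**7. What remains for the arm comparison.** AEs go on the source data worksheet (8.4.2.1) and from there to the trial database (12.3). The safety endpoint is adverse effects on the UKU scale (4.1.4), rated at baseline and visits 1 to 3 (4.3). CAARMS and HADS are also rated at those visits. Counts by arm therefore remain available for most listed events. Worsening psychotic symptoms are the exception under step 4, although CAARMS measures them as the primary outcome.

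**The case against.** The strongest reply is that the list governs reporting and not capture. All AEs are recorded and entered in the database, and suicidal thoughts are also notified to the clinical team and monitored. The safety endpoint depends on neither causality ratings nor expedited reports. The data monitoring committee has continuing access to unblinded safety data (12.9.4), and the trial manager is unblinded so that safety data reach its chair quickly (11.2.2). Hospitalisation for worsening remains an SAE. The list is headed as AEs, so extending it to SAEs is an inference from the exception.

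Most of this stands, and it rules out several stronger readings:

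- A reader might infer that the safety comparison is hollowed out or biased towards a finding of safety. Step 7 shows otherwise: a comparison of arms needs counts, not individual causality ratings, and most counts survive.
- A reader might infer that all such events are lost. The advance classification touches causality and onward reporting, not recording, and the protocol gives no event rates from which to size a loss.
- A reader might infer that sites are told to enter a negative causality rating. No section says so or suspends the per-event question.
- A reader might see somnolence and decreased weight in the second list as contradicting sleep and appetite disturbances in the first. The terms differ, and the protocol does not equate them.
- A reader might take 8.4.3 to end all follow-up. Section 8.4.2 still has unresolved AEs followed as medically indicated and SAEs followed to outcome. The conflict concerns trial data, and arises only if the trial stops early.

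The reply does not remove the conflict over causality, the exception with no limit on seriousness, or the two incompatible recording rules. UKU ratings at four scheduled visits do not replace prompt reporting of a serious event.

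**Conclusion.** The concern holds for causality classification and for onward SAE/SUSAR reporting. Section 8.4.2.2 contradicts the per-event assessment in 8.4.2 for seven event types. Section 8.4.2 gives two SAE rules that diverge for serious events on that list. That a site would withhold a serious event depends on its reading the exception together with the list. The text permits this reading but does not compel it.

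Two further contradictions are plain on the page: whether worsening of the primary condition is recorded as an AE, and whether AE data are collected to day 212 after early termination.

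The size cannot be given as a number. The between-arm safety comparison remains largely intact, which assumes that sites follow the rule in 8.4.2.1 to record every AE. The correction is a matter of wording, but it bears on the sponsor's safety oversight and should be made.

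**What to change.** Reconcile 8.4.2, 8.4.2.1, 8.4.2.2 and 8.4.3 as follows.

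1. In the first list of 8.4.2.2, remove the advance statement that the events are unrelated and describe them as anticipated in this population. Avoid the word expected: 8.4.2 defines expectedness against the Investigator's Brochure, and it drives SUSAR classification. State that each recorded event keeps its own causality rating and that recorded events are tabulated by arm.
2. Limit both the non-reporting list and the exception in 8.4.2 to non-serious events not suspected to be related. The general SAE rule and the hospitalisation rule then stand without conflict.
3. State once, in the same terms in 8.4.2 and 8.4.2.2, whether worsening of the primary condition is recorded as an AE. Changing 8.4.2.2 alone would leave the contrary sentence in 8.4.2 in force.
4. In 8.4.3, state that AE and SAE collection for exposed participants continues to the final safety record review.

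The cost is protocol wording, more background psychiatric events in the listings, and somewhat more site paperwork. The fourth change adds little, because the final safety visit is already a review of medical records.
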